## Inclusion and Exclusion Criteria

Describe the criteria that define who will be included in your final study sample.

1. Must be at least 18 years of age
- 2- Currently on suboxone therapy
3. Patients with English as their primary language

Describe the criteria that define who will be **excluded** from your final study sample.

1. Less than 18 years of age
2. Not treated with suboxone.
3. Non-English speaking patients

*Indicate whether you will include non-English speaking individuals in your study. Provide justification if you will exclude non-English speaking individuals.*

The intervention in our study involves educational information regarding different aspects of hepatitis C including pathogenesis, diagnosis and treatment. This material will be only presented in English, therefore only patients who are able to comprehend English language would be able to complete the study pre-and post-test instrument as well as questionnaire to measure the effectiveness of the intervention.

## **Procedures Involved**

We plan to conduct a study involving 2 groups. One group consists of the intervention subjects and other of the control subjects. The intervention subjects will receive the computer-based video education, while the “control group” will receive the brochure-based intervention. The goal is to evaluate the effect of education on health literacy in people with hepatitis C and currently on opiate replacement therapy. We also plan to evaluate the willingness for treatment in people with active hepatitis C infection.

We will start with a feasibility survey to assess the patient demographics at all clinic sites where this study will be conducted. We will also conduct cognitive testing of the survey instruments to be administered to ensure reliability and accuracy. We will also request that patient partners and subject matter experts provide guidance on the educational intervention to be delivered. The study flyers for advertisement will be distributed at all the clinic sites. Patients will be given information about the study. In case of agreement to participate, informed consent will be obtained. After enrollment of the population of interest, we will start the retrospective chart review in order to extract information about patient demographics, which will include age, gender, race/ethnicity, educational status, marital status, and a history of mental health problems, information about substance abuse & status of hepatitis C, occupational and employment status.

After that information is collected, we plan to designate the population in 2 groups i.e. Intervention & Control. The next step will be the educational intervention in group A which will consist of distribution of HCV educational brochure. Similarly group B will have the video class intervention on the computer administered by an on-site facilitator. These interventions will occur after the pre-test assessment by a designed questionnaire which will include questions on different aspects of hepatitis-C infection disease processes. Finally, we will administer a post interventional assessment with the same questionnaire used for pre-intervention assessment. For patients with history of HCV infection irrespective of treatment, an additional section will be added to check their willingness for treatment.

## **Study Timelines**

The anticipated time frame review of the records is up to 1-2 months. We estimate it will take 12 months to complete enrollment in the study.

## **Risks to Subjects**

This study involves only minimal risk to study participants. Breach of confidentiality is the primary potential risk. However, the data will be kept in secure, encrypted, password-protected flash drives made available only to study personnel. All study personnel are well-versed in

HIPAA compliance and use the electronic medical record on a daily basis. Moreover, study personnel are CITI trained in HIPAA compliance.

| | |
|------------------------------|---|
| Official Title: | Hepatitis C-Video vs. Brochure Education Delivery |
| NCT number: | NCT04204447 |
| Document Type: | Statistical Analysis Plan |
| Date of the Document: | June 30, 2018 |

Statistical Methods

We will initiate the activities on this study with collection of patient demographics at all sites. As part of the preparatory work, we will conduct cognitive testing of the survey instruments to be administered to ensure reliability and accuracy.

The population will be designated into 2 groups i.e. Intervention & Control. The intervention will have the video class intervention and the control will read an HCV educational brochure. We will design both interventions to assess the level of HCV knowledge. Information provided by the brochure and the video will be assessed by the pre/post test questions. These interventions will occur after the pre-test assessment by a designed questionnaire which will include questions on different aspects of hepatitis-C infection disease processes. The last step before analysis will be post interventional assessment with the same questionnaire used for pre-intervention assessment administered 1 month (+/- 2 weeks) after the intervention. All of the intervention and assessment tools will be validated before use. The second assessment may be done over the phone if the subject has no scheduled visits to the clinic during the follow-up period.

At the end we do plan to utilize the data for analysis and manuscript preparation.

Description of the clinics: The two clinics are approximately the same in terms of the percentage of rural patients, of rural HCV seropositive patients, and in the gender distribution. Because patient characteristics differ on the basis of age, race, and ethnicity, we will perform 1:1 matching of the subjects, if possible from the two clinics on these variables.

Statistical analysis: We will conduct exploratory data analysis using box plots for comparison between distributions of continuous variables. Histograms also will provide an additional way of comparing these distributions. Continuous variables are going to be summarized by means and standard deviations or medians and interquartile range, as appropriate. Discrete, that is, categorical variables will be summarized by proportions.

To understand the impact of clinic and individual patient characteristics on the HCV seropositive individuals, we will begin with building logistic regression models. If the outcome variable is defined as "1" when an HCV seropositive individual is identified and "0" otherwise, logistic regression will provide the association of HCV seropositivity as a function of clinic and individual characteristics. Further, to understand the changes in these percentages over time, we will perform a trend analysis at the minimum.

We will test the differences between the scores obtained on the post-intervention assessment and the 1-month follow up assessment. We will assess the distribution of the scores. Modeling will be done using generalized linear mixed-effects models or an alternative appropriate approach. We will include demographic factors and other covariates as appropriate.

Power/Sample Size:

The following table shows the sample size needed per group, as a function of the difference in the proportion of patients from both clinics who appear for the first appointment and the desired power of the test. The level of significance is 0.05.

| Differences in proportions | Power | |
|----------------------------|-------|------|
| | 0.80 | 0.90 |
| 0.10 | 293 | 392 |
| 0.15 | 138 | 184 |
| 0.20 | 81 | 108 |

| | | |
|------|----|----|
| 0.25 | 54 | 72 |
| 0.30 | 39 | 51 |

Thus, if our difference is 20% between those who make the first appointment for an HCV evaluation in the clinic that receives the SAMHSA brochure and the full education groups, we will need 81 patients per group (total 162) to have an 80% power.

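### The one-month knowledge test may be taken by phone, and nothing in the plan asks phoned brochure patients to answer without the brochure

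*SAP*

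**What the plan says.** The SAP (Statistical Methods) has the follow-up questionnaire "administered 1 month (+/- 2 weeks) after the intervention", and then allows a change of mode: "The second assessment may be done over the phone if the subject has no scheduled visits to the clinic during the follow-up period". The individual subject's visit schedule therefore decides whether the phone may be used, and nothing fixes the date within the window. The questionnaire is the one used before the intervention, and its questions test the content of the brochure and the video.

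The two materials differ in how easily a patient could take them home. The Protocol (Procedures Involved) describes one intervention as "distribution of HCV educational brochure" and the other as a video class on a computer with a facilitator on site. That section swaps the group letters used under Study Design, so the arms are named here by their material. The SAP says that the control group reads the brochure. Neither document says whether patients keep it.

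For the scores, the SAP plans mixed-effects models or an alternative, with demographic and other covariates as appropriate. It does not name assessment mode or days since the intervention for this model, and neither document says that they will be recorded.

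On arm and clinic, the SAP says "we will perform 1:1 matching of the subjects, if possible from the two clinics on these variables", and Power/Sample Size refers to first appointments "in the clinic that receives the SAMHSA brochure". The Protocol says only that patients are put into two groups after enrolment and chart review, and expects up to 2-3 clinics.

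**The concern.** The Protocol (Study Design) defines the outcome as the percentage of patients who retain knowledge of hepatitis C. A test taken with the source material at hand does not measure retention. If some brochure patients can take it that way and video patients cannot, the two arms are not given the same test. The error would favour the brochure and so work against the Protocol's hypothesis that video does better: a real advantage of video could be understated or missed.

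Delay is the second strand. Retention depends on how long after teaching it is tested, and the longest permitted delay is nearly three times the shortest. If mode or delay differs between arms, the comparison can shift in either direction.

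**Working it through.** **1. The plan's own figure, and what it sizes.** Inputs from Power/Sample Size: "The level of significance is 0.05"; a 20-point difference in first-appointment attendance; 80% power; 81 per group. Sidedness and baseline rate are not stated. A two-sided test with a baseline of 0.20 fits every row of the table to within one patient. With rates of 0.20 and 0.40 (mean 0.30):

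n = [1.960 × √(2 × 0.30 × 0.70) + 0.842 × √(0.20 × 0.80 + 0.40 × 0.60)]² / 0.20² = 81.2.

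The stated 81 is reproduced. It concerns attendance, not the knowledge score, so it neither supports nor refutes this point.

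**2. The window.** Taking a month as 30 days, 30 − 14 = 16 and 30 + 14 = 44 days. The ratio is 44/16 = 2.75.

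**3. Open-book bias.** The documents give no phone share, no rate of consulting the brochure, no gain from doing so and no score SD. All inputs below are assumptions: 20-60% of brochure patients phoned, 25-50% of those consulting the brochure, and a gain of 0.3-0.8 SD.

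Bias toward brochure = share phoned × share consulting × gain

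- Low: 0.20 × 0.25 × 0.3 = 0.015 SD
- Midpoints: 0.40 × 0.375 × 0.55 = 0.083 SD
- High: 0.60 × 0.50 × 0.8 = 0.24 SD

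The phone share in the video arm does not enter. The bias needs no difference in phone share, and no link between clinic and arm.

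**4. Added imbalance, only if mode or delay differs between arms.** Inputs are again assumed.

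- Mode: a difference in phone share of 10-50 points × a mode effect of 0.1-0.5 SD gives 0.01 to 0.25 SD (30 points × 0.3 SD = 0.09 SD).
- Delay: a difference in mean delay of 0.5-2 weeks × a loss of 0.02-0.10 SD per week gives 0.01 to 0.20 SD.

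Both are zero if mode and delay are balanced between arms or do not affect the score.

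**5. Would a mode covariate remove the open-book bias?** Suppose phoned brochure patients gain 0.25 SD on average, video patients gain nothing, and the true arm effect is zero. A model with arm and a mode main effect averages the arm difference over the two modes. With equal-sized arms, and b and v the phone shares in the brochure and video arms, the weights are bv/(b + v) for phone and (1 − b)(1 − v)/(2 − b − v) for clinic.

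- b = v = 0.40: weights 0.20 and 0.30, so the phone weight is 0.40. Bias is 0.40 × 0.25 = 0.100 SD before adjustment and 0.100 SD after.
- b = 0.50, v = 0.20: weights 0.143 and 0.308, so the phone weight is 0.317. Bias falls only from 0.50 × 0.25 = 0.125 SD to 0.317 × 0.25 = 0.079 SD.

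A gain confined to one arm is an arm-by-mode interaction, and a main effect leaves most or all of it in place.

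**6. Precision of the sensitivity analyses**, for phone share p, equal in both arms. The in-clinic-only standard error is larger by 1/√(1 − p): 1.12 times at 20% phoned and 1.58 times at 60%. The standard error of the arm-by-mode term is 1/√(p(1 − p)) times that of the overall arm difference: 2.04 times at 40%.

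**The case against.** The open-book mechanism rests on little text. The Protocol distributes the brochure and the SAP has patients read it; neither says that they take it home. The SAP also says that intervention and assessment tools will be validated before use. A phone fallback and a window of two weeks either side are sensible ways to limit loss to follow-up. All of this stands, and it is why the point is put as a possibility. It does not close the gap: the documents do not mention phone and in-clinic equivalence, and validating a questionnaire does not stop a respondent looking up the answers.

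Three stronger readings are tempting, and the documents do not support them.

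- A reader might infer that clinic defines the arm, and that each clinic's schedule therefore drives mode and timing. The phone rule is set per subject. No passage says that visit schedules differ between clinics or that the test date follows visits. Arm by clinic is implied in the SAP but never given as the allocation rule.
- A reader might infer that the score analysis is unadjusted. The SAP does plan covariates; the gap is that mode and delay are neither named nor said to be recorded.
- A reader might set the bias against 81 per group. That size detects about 0.44 SD at 80% power in a two-sample t-test, and a bias of 0.083 SD would leave about 63%. But 81 was chosen for attendance, the Protocol's knowledge outcome is a percentage, and no document plans for 0.44 SD. This loss of power is not a property of the plan.

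**Conclusion.** The concern holds in limited form. As written, the plan lets the retention test be taken in clinic or by phone, according to the individual subject's visits, at any point from about 2 to 6 weeks. It gives a brochure to one arm only and has no safeguard against its use during a call. That can bias the comparison toward the brochure even with equal phone shares.

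Under the assumed inputs the open-book bias ranges from about 0.02 to 0.24 SD, with about 0.08 SD at the midpoints. It is zero if patients do not keep the brochure or do not consult it. The documents cannot narrow this range. They also cannot turn it into percentage points on the Protocol's outcome, because they give neither a score distribution nor a cut-off for retention. Further bias from unequal mode or delay is conditional: it needs an actual difference between arms, which would be more likely if arm follows clinic.

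**What to change.** - Apply the same rule for mode and for timing within the window in both arms.
- Open each phone assessment with a scripted request to answer without the brochure or notes.
- Record mode and date for every follow-up assessment.
- Report phone share and days since the intervention by arm.
- As sensitivity analyses, report the arm effect by mode, using an arm-by-mode term, and the arm effect among in-clinic assessments only.

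The SAP should also state how arm is allocated and whether patients keep the brochure, since these decide how far the concern reaches.

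The cost is one script line, two data fields and two further analyses. The script matters most, because it acts at source, although compliance on a call cannot be verified. The sensitivity analyses are less precise than the main comparison, so a non-significant arm-by-mode term would not show that the bias is absent. Mode and delay arise after the intervention, and patients with a scheduled visit may differ from those without one, so the in-clinic subset may be selected. A mode main effect alone is not a substitute: it would not remove an open-book gain confined to the brochure arm. None of these analyses removes confounding of arm with clinic, if arm does follow clinic.

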## Study Design

We will start with a retrospective chart review to extract information about patient demographics, which will include age, gender, race/ethnicity, educational status, marital status, and history of mental health problems, information about substance abuse & status of hepatitis C, occupational and employment status. Some of this information will be required to decide matching factors between the clinics.

We will employ an observational two-group method design to evaluate the effect of video or computer-based education as a determinant of seeking treatment for HCV among patients on opioid agonist therapy (OAT). Group A will receive the video class intervention on the computer administered by an on-site facilitator, while “group-B” will receive an HCV educational brochure. The two groups are matched in 1:1 fashion to make the two groups similar with respect to the certain key characteristics, such as race, sex, age etc. The outcome variable is the percentage of the individuals in the two groups that retain HCV-knowledge. We expect up to 2-3 clinics to participate.

These intervention will occur after pre-test assessment by a designed questionnaire, which will include questions from different aspects of hepatitis-C infection disease process. Patients will not be notified of their questionnaire score. We will assess the questionnaires reliability and accuracy among a patient sample drawn from the clinics where the questionnaires will be deployed. We will also convey a committee of experts who will provide input on the design of the educational intervention. The last step before analysis will be post interventional assessment with the same questionnaire used for pre-intervention assessment. At the end of the study, we plan to utilize the data for analysis and manuscript preparation.

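### The SAP's only named test of the knowledge scores compares what its own schedule makes a single assessment, and no video-versus-brochure contrast is written for the scores

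*SAP*

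**What the plan says.** **Schedule.** The SAP's Statistical Methods section places a pre-test before the intervention and then a "post interventional assessment with the same questionnaire used for pre-intervention assessment administered 1 month (+/- 2 weeks) after the intervention". It adds: "The second assessment may be done over the phone", for patients with no clinic visit due in the follow-up period. It also says that the pre/post questions are the means of assessing what the brochure and the video convey. The protocol describes the same two occasions without timing the later one. Study Design has "The last step before analysis will be post interventional assessment with the same questionnaire used for pre-intervention assessment", and Procedures Involved has "Finally, we will administer a post interventional assessment with the same questionnaire used for pre-intervention assessment".

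**Score analysis.** The Statistical analysis part of the SAP has four sentences on the scores. The first names a test: "We will test the differences between the scores obtained on the post-intervention assessment and the 1-month follow up assessment". The second promises a look at the data: "We will assess the distribution of the scores". The third turns to the model and keeps it open: "Modeling will be done using generalized linear mixed-effects models or an alternative appropriate approach". The last deals with adjustment, also left open: "We will include demographic factors and other covariates as appropriate".

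**Trial question.** The protocol's Hypothesis section expects better literacy and decision-making with video than with a brochure. Its Study Design section defines the outcome as the percentage in each of the two groups who retain knowledge of hepatitis C.

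**The concern.** The score paragraph and the schedule do not fit together. The paragraph treats the post-intervention and one-month assessments as two occasions; the schedule has one assessment after the intervention, and it takes place at one month. The pre-test, which the SAP says is part of how the education is assessed, does not appear in the named test. Neither do the two education groups.

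The answer to the trial's main question is at stake. A change in scores over time, in either direction, does not show that one format works better than the other. Because the group contrast is unwritten and the model and covariates are left open, the comparison that does answer the question could be chosen after the data are seen.

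**Working it through.** The documents give no figure for the scores: no SD, expected gain, correlation or target difference. The SAP's sample-size table (81 per group for a 20-point difference at 80% power) concerns attendance at a first appointment, so it offers nothing to reproduce here. The check is a comparison of texts.

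1. **Count the occasions.** The SAP has a pre-test and one post-interventional assessment at one month, give or take two weeks, and then refers to the second assessment. Both protocol sections have one pre-test and one post-test. All of these point to two occasions.

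2. **Place the named test on that schedule.** Its first score is the post-intervention score and its second is the one-month score. With two occasions, both are the later one. The difference is then zero for every patient by definition, and there is nothing to test.

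3. **Try the two natural repairs.** Let the mean change in score be g_V in the video group and g_B in the brochure group.
   - *An immediate post-test was meant.* The change runs from immediate to one month. This bears on retention, but the assessment is not scheduled, the pre-test is unused and no group is named.
   - *The pre-test was meant.* The change runs from pre-test to one month. Again no group is named.
   - Under either repair, a test over time addresses g_V and g_B separately, or their average if the groups are combined; the SAP does not say which. The hypothesis concerns g_V − g_B. If g_V = g_B = g and g is not zero, there is a real change over time to detect while g_V − g_B = 0. If g_V = −g_B, the equal-weight average change is zero while the formats differ by 2g_V. Finding significance in one group and not in the other is not a test of the difference either.

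4. **Look for the contrast elsewhere in the SAP.** The plots and summaries are descriptive. The logistic regression and the trend analysis concern HCV seropositivity. The Power/Sample Size section does compare brochure with full education, but on appointment attendance. The mixed-model sentence states no group, time or group-by-time term, and the covariate sentence does not list group. No video-versus-brochure contrast for the scores is written anywhere.

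5. **Check what a replacement contrast would estimate if each clinic receives one format.** Assume no format effect, a clinic difference c present equally at both times, equal SDs, and pre/post correlation ρ. The expected group difference is c for the raw one-month score, c(1 − ρ) after adjustment for the pre-test, and c − c = 0 for the difference in change. Adjustment for the pre-test therefore reduces a stable clinic difference without removing it. The difference in change removes it, but only because it is constant over time. This is a separate confounding problem, but it bears on how the replacement is written.

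**The case against.** The strongest reply has three parts.

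- **An immediate post-test may exist.** Calling the one-month assessment the last step does not rule out an earlier one, and an outcome about retaining knowledge fits a comparison of immediate with one-month scores. This stands in part. A reader might infer that the named test can never be run; the documents support only that it cannot be run on the schedule they set out. Against the reply, the SAP calls the later assessment the second, and neither document schedules a third.

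- **The between-group intent is plain.** The hypothesis, the two-group outcome and the designation of intervention and control all point to it, and a mixed model would naturally carry a group term. This also stands in part. A reader might infer that the formats will not be compared on the scores at all; the documents do not support that. But intent does not choose between one-month score, change and percentage retaining, and these can give different answers in a matched, non-randomised design.

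- **No error rate can be attached.** This stands in full. A reader might pool the groups, assume a gain, and quote the chance of a significant before/after result as a false-positive rate for video. The SAP does not say the groups are pooled and supplies no inputs. Such a figure would in any case be power to detect a real change over time.

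**Conclusion.** The point holds as an inconsistency together with an omission. On the schedule in the SAP's Statistical Methods section, the only named score test compares one assessment with itself. Under either plausible repair it tests change over time with no group named. The contrast that matches the hypothesis could sit in the mixed model but is not written, and the modelling sentences leave room to settle it late.

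The defect is structural and carries no magnitude. The conclusion rests on reading the schedule as two occasions, which is what both documents describe. If a third occasion was intended, the schedule needs correcting instead, and the missing group contrast remains. The point covers the knowledge half of the hypothesis only; decision-making is not addressed here.

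**What to change.** 1. Reconcile the SAP's Statistical Methods and Statistical analysis sections on how many assessments there are and when each is given.
2. Replace the named test with a pre-stated video-versus-brochure contrast that uses the pre-test already planned. It may be the group difference in one-month score adjusted for pre-test, or the group-by-time contrast (difference between groups in pre-to-one-month change). Fix the choice before the data are seen, account for the 1:1 matching, and report the estimate with its 95% CI.
3. The Power/Sample Size section speaks of the brochure as going to a clinic, which suggests that each clinic may receive only one format. If so, state that group and clinic are confounded and limit the conclusion accordingly. Report the difference in change at least as a pre-stated companion analysis, noting that it removes only a clinic difference that is constant over time.
4. If an immediate post-test is in fact given, schedule it and compare immediate-to-one-month retention between the groups.

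The cost is a rewritten SAP paragraph and two decisions, on schedule and on contrast, plus the confounding statement if item 3 applies. The pre-test and one-month scores are already planned, so no new data are needed unless an immediate post-test was intended.

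### The SAP gives the pre-test HCV knowledge score no stated role in the score analysis; if it is left out, the non-randomised comparison at 1 month can be biased and loses precision.

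*SAP*

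**What the plan says.** - **Design.** Protocol, Study Design: "We will employ an observational two-group method design". Neither document describes randomisation. Protocol, Procedures Involved, places group formation after the chart review: "After that information is collected, we plan to designate the population in 2 groups i.e. Intervention & Control". The SAP's Power/Sample Size text suggests that format may follow clinic, since it speaks of attendance "in the clinic that receives the SAMHSA brochure and the full education groups".
- **Matching.** SAP, Description of the clinics, names age, race and ethnicity and then says "we will perform 1:1 matching of the subjects, if possible from the two clinics on these variables". Protocol, Study Design, has an open list, "with respect to the certain key characteristics, such as race, sex, age etc", and draws matching factors from a chart review whose listed items include no knowledge score.
- **Pre-test.** SAP, Statistical Methods: "These interventions will occur after the pre-test assessment by a designed questionnaire". The same questionnaire is used again at 1 month, give or take 2 weeks. The section also says that pre- and post-test questions will assess the information delivered, but ties this to no model.
- **Score analysis.** The modelling paragraph under Statistical analysis tests post-intervention against 1-month scores, using generalized linear mixed-effects models or an alternative. On covariates it says only "We will include demographic factors and other covariates as appropriate". It does not mention the pre-test and writes out no contrast between video and brochure.

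**The concern.** A knowledge score taken on the same instrument before education is likely to be among the best predictors of the later score. Matching on age, race and ethnicity does not ensure that two sets of patients start with the same HCV knowledge. If format follows clinic, prior knowledge could differ through, for example, local counselling, and the better-informed clinic's format would then look more effective. Even with no imbalance, leaving out a correlated baseline score widens the confidence interval.

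In a non-randomised comparison the choice of main adjustment should be fixed before the data are seen. An open covariate clause leaves it to be made afterwards.

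**Working it through.** **The plan's own figure.** The Power/Sample Size table gives 81 per group for a 20-point difference in first-appointment attendance at 80% power. The reference proportion is not stated. With an inferred 0.20, two-sided 0.05 and pooled variance:

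n = [1.960·√(2·0.30·0.70) + 0.842·√(0.20·0.80 + 0.40·0.60)]² / 0.20² = 81.2.

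All ten cells of the table reproduce to within rounding in the same way. That calculation concerns attendance, not scores. The 81 is used below only as the planned group size.

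**Inputs for the score comparison.** From the SAP: 81 per group and a 0.05 level (taken as two-sided). Assumed, because the documents are silent: score SD of 1 (standardised units), pre-test to 1-month correlation r of 0.4 to 0.7, baseline imbalance d of 0.1 to 0.5 SD, and no true format effect. Normal approximations are used throughout.

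The standard error of the 1-month difference without the pre-test is √(2/81) = 0.157 SD.

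**Case A: the baseline difference fully persists to 1 month.** Without the pre-test, bias = d. It is assumed that demographic adjustment explains none of d.

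| d (SD) | d / 0.157 | Rejection rate (nominal 5%) |
|---|---|---|
| 0.1 | 0.64 | 10% |
| 0.2 | 1.27 | 25% |
| 0.3 | 1.91 | 48% |
| 0.5 | 3.18 | 89% |

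With the pre-test as covariate, bias = (1 − r)·d and SE = 0.157·√(1 − r²). At d = 0.3:
- r = 0.4: bias 0.18 SD, SE 0.144, rejection 24%
- r = 0.6: bias 0.12 SD, SE 0.126, rejection 16%
- r = 0.7: bias 0.09 SD, SE 0.112, rejection 13%

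The between-group difference in change from pre-test has zero bias in this case.

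**Case B: within groups, the 1-month score depends on the pre-test with slope r, and there is no other group difference.** Without the pre-test, bias = r·d. At d = 0.3:
- r = 0.4: bias 0.12 SD, rejection 12%
- r = 0.6: bias 0.18 SD, rejection 21%
- r = 0.7: bias 0.21 SD, rejection 27%

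With the pre-test as covariate the bias is zero. The change-from-pre-test contrast is now the biased one, by (r − 1)·d: −0.18, −0.12 and −0.09 SD.

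**Precision with balanced groups.** The difference detectable at 80% power is (1.960 + 0.842)·0.157·√(1 − r²):
- pre-test omitted: 0.44 SD
- pre-test as covariate: 0.40 SD (r = 0.4), 0.35 SD (r = 0.6), 0.31 SD (r = 0.7)

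Residual variance falls by r², that is by 16%, 36% and 49%.

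**The case against.** The best counter-argument is that the plan does not rule the pre-test out. The covariate clause extends beyond demographics, the protocol's matching list is open-ended, and a mixed model could take the pre-test as a repeated response without naming it as a covariate. The SAP clearly means to use pre- and post-test questions in some way. All of this stands. It means that bias and lost precision are possible, not certain, but it does not amount to a pre-specified analysis.

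A reader might infer that prior knowledge stays uncontrolled whatever contrast is chosen. That is wrong. A between-group difference in change from pre-test removes a stable baseline difference. So would a between-group difference in the one change the SAP writes down, from post-intervention to 1 month. That second contrast needs a separate earlier post-test. SAP Statistical Methods describes the post-intervention assessment as the one given at 1 month, so it is unclear whether an earlier one exists. If it does, the contrast measures retention after education, not the gain from it.

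It is also fair to object that covariate adjustment is not a complete remedy. In Case A it leaves 0.12 SD of bias at r = 0.6, where the change contrast leaves none. In Case B the reverse holds. Without randomisation the data cannot settle which case applies, which is a reason to show both analyses.

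Finally, it is tempting to read the protocol as forming groups from chart data alone and to ask for the pre-test to be moved earlier. Procedures Involved does not say alone, nor whether the pre-test comes before or after designation. The remedy needs no change of procedure.

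**Conclusion.** The point holds as a gap in pre-specification. The pre-test is collected on everyone with the outcome instrument, yet the SAP assigns it no role, and the between-group comparison at 1 month is itself left to inference.

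The possible size depends on the assumed imbalance and on how it carries forward. If the pre-test is omitted, rejection under no format effect runs from about 10% (0.1 SD) to 89% (0.5 SD) with full persistence. At 0.3 SD it is 12% to 27% under the slope assumption. The 48% figure belongs to a single assumed imbalance and should not be quoted without this range. The precision loss is the gap between 0.44 SD and 0.40 to 0.31 SD detectable, for correlations of 0.4 to 0.7.

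The documents do not support two stronger conclusions that a reader might draw: that the knowledge comparison will be biased, or that 81 per group is invalid. The first depends on a modelling choice not yet made. The second concerns a number derived for appointment attendance.

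**What to change.** In the modelling paragraph of the SAP's Statistical analysis section:

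1. State that the between-group comparison of 1-month scores includes the pre-test score as a covariate, alongside education format, age, race and ethnicity.
2. Report the standardised pre-test difference between the groups.
3. Report the between-group difference in change from pre-test alongside the adjusted result, and say that the two rest on different assumptions about how a baseline difference carries forward.

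The SAP should add that neither analysis removes other confounding by clinic.

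The cost is a sentence or two in the SAP, one line in the baseline table and one further contrast in the results. No new data are needed, and the order of study procedures stays as it is.
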